## 13 STATISTICAL CONSIDERATIONS

### 13.1 Study Design/Endpoints

This is a multi-center, open-label, non-randomized, two stage, phase II study of trametinib in patients with relapsed or refractory MM. BM samples from patients will be analyzed for NRAS, KRAS, BRAF mutations (next generation sequencing) at baseline visit. Patients will be stratified into one of two study groups:

- Biomarker positive (NRAS, KRAS, BRAF mutated as defined in [Appendix F](#))
- Biomarker negative (without NRAS, KRAS, BRAF mutation)

Patients will be independently recruited into either of the two groups based on biomarker positivity.

This study will use a two-stage design for both patient groups. Each group will enroll 12 patients in the first stage and an additional 25 patients in the second stage, if the pre-determined response criteria are met during the first stage. The target enrollment is a minimum of 24 evaluable subjects and a maximum number of 74 if both groups accrue to the second stage.

Individual patients will receive a minimum of 2 cycles and may remain on treatment as long as there is no evidence of disease progression or unacceptable toxicity or patient/physician decision to discontinue. As a secondary objective, patients who develop progressive disease on trametinib monotherapy or achieve less than a PR after 4 cycles of treatment will have the option to continue on GSK2141795 supplemented trametinib regimen. The dosing of trametinib and GSK2141795 will be according to the recommended 1.5 mg trametinib and 50 mg GSK2141795 daily dosing schedule. The M-protein level at the time of addition of GSK2141795 will be considered the new baseline, and the patients will be allowed to continue the new treatment schedule until further progression, toxicity, or patient/physician decision to discontinue.

The UHN Data Safety and Monitoring Board (DSMB) will evaluate the safety of the trial after completion of enrollment of the first 24 patients and/or biannually during phase II. If greater than 20% of subjects experience grade 4 diarrhea or rash despite optimal management or if greater than 10% subjects experience RPEd or RVO or  $\geq 3$  pneumonitis, a detailed review of these toxicities will be performed by an independent safety committee to determine whether the trial should be stopped.

**The primary objective is** to evaluate the antitumor activity of trametinib determined by overall response rate (ORR), in groups of patients with relapse or refractory multiple myeloma that are:

- Biomarker positive (NRAS, KRAS, BRAF mutated as defined [Appendix F](#))
- Biomarker negative (without NRAS, KRAS, BRAF mutation)

The endpoint for the primary objective, ORR, is evidenced by confirmed response rate, defined as number of patients with partial response or better by IMWG criteria divided by the number of patients in the applicable group (biomarker positive or negative). All patients included in the study will be assessed for response to treatment, even if there are major protocol treatment deviations or if they are ineligible (see section 13.5.2). The patient will be classified as having had a response if he/she has a confirmed response per the definitions in section [11.2.2](#). (i.e., a stringent complete response, or complete response or near complete response or very good partial response or partial response noted as the objective status of two consecutive assessments). The rate of minor response (MR) and progressive disease (PD) will also be observed.

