#### **AEs of special interest:**

Rash, diarrhea, visual disorders, hepatic disorders, cardiac-related AEs, and pneumonitis are considered AEs of special interest because they are either known class effects (*i.e.*, have been observed with other MEK inhibitors) or are potentially life-threatening (Investigator's Brochure, 2012a).

Rash: Rash was a common AE observed across different dose levels and in different

combinations (Investigator's Brochure, 2013). At the 2 mg dose, rash was seen in 27% to 78% of patients in different trials. Of the ~370 subjects with rash AEs at the 2 mg monotherapy dose (including crossover subjects) in five studies, the majority of rash AEs were grades 1 or 2 (24% to 73%); 0% to 9% of patients experienced grade 3 rash AEs, and four patients had a grade 4 rash AE.

In a randomized phase 3 trial of trametinib vs. chemotherapy, the overall incidence of skin toxicity (including rash, dermatitis, acneiform rash, palmar-plantar erythrodysesthesia syndrome, and erythema) was 87% in patients treated with trametinib and 13% in chemotherapy-treated patients. Severe skin toxicity occurred in 12% of patients on the trametinib arm, most commonly for secondary infections of the skin. The median time to onset of skin toxicity was 15 days (range: 1 to 221 days), and median time to resolution was 48 days (range: 1 to 282 days). Dose reduction was required in 12% for skin toxicities, and permanent discontinuation of trametinib was required in 1% of patients.

Diarrhea: At the 2 mg monotherapy dose, 33% to 58% of patients in five trials had diarrhea (Investigator's Brochure, 2013). Of ~320 subjects (including crossover subjects) with diarrhea at this dose, the majority of diarrhea AEs were grade 1 or 2 in severity (33% to 56% of all study patients); 17 patients had grade 3 diarrhea, and none had grade 4 diarrhea.

Visual disorders: At the 2 mg monotherapy dose, 4% to 21% of the patients in five trials experienced visual disorders (Investigator's Brochure, 2013). Of the 85 total subjects (including crossover subjects) experiencing visual disorders at this dose level, the majority of visual disorders were grades 1 or 2 (4% to 20% of all study patients); six patients experienced grade 3 visual disorders, and one patient experienced a grade 4 visual disorder.

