#### 2.2.1.5 Clinical Experience with the Combination of Trametinib + GSK2141795 (AKT inhibitor) (TAC113886)

Twenty-three patients with advanced solid tumors received the combination using a zone-based escalation procedure enabling evaluation of multiple combination doses in parallel cohorts (Kurzrock *et al.*, 2011). While the RP2D for single agent for single agent trametinib and GSK2141795 are 2 mg/d and 75 mg/d, dose reductions were required for the combination. DLTs include grade 2 AST and ALT elevation, and grade 3 chest pain with sustained ventricular tachycardia; all DLTs were reversible with drug interruption. The most common AEs ( $\geq 10\%$ ) included nausea (26%), AST elevation (22%; grade 3/4, 9%), fatigue (22%) and rash (22%). Three MTDs were defined for variable dose ratios: 2 mg trametinib + 25 mg GSK2141795; 0.5 mg trametinib + 75 mg GSK2141795; and 1.5 mg trametinib + 50 mg GSK2141795. Three of 13 evaluable patients (unselected) had tumor shrinkage of 8% (ovarian), 16% (endometrial), and 17% (ovarian) after 8 weeks on study. The dose regime of 1.5 mg trametinib + 50 mg GSK2141795 will be considered for further development. Additional trials to explore alternate schedules (*e.g.*, intermittent) and pharmacodynamic markers are ongoing.

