#### 5.2.4 Prophylaxis medications

The following medications are recommended as prophylaxis during the first 4 cycles of treatment due to an increased incidence of Shingles and infection noted on patients in this trial:

- Shingles prophylaxis: Valtrex 500mg OD is preferred otherwise acyclovir 400mg bid can be used

- Infection prophylaxis: Ciprofloxacin or Moxifloxacin

The prophylaxis recommendations above are an additional care measure while determination as to whether there is reasonable possibility, that Trametinib and GSK2141795 caused the increased incidence of shingles or infection (urinary tract or upper respiratory) noted in the patients on this trial.

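### The numeric safety triggers in section 13.1 use one undefined denominator, so an excess on trametinib plus GSK2141795 can be diluted by patients who have not crossed over

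*Combined protocol and SAP*

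**What the plan says.** Section 13.1 has the UHN DSMB review safety on a schedule: it "will evaluate the safety of the trial after completion of enrollment of the first 24 patients and/or biannually during phase II". It then gives the only numeric safety rule for the trial as a whole, in two limbs:

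- "If greater than 20% of subjects experience grade 4 diarrhea or rash despite optimal management";
- "if greater than 10% subjects experience RPEd or RVO or" pneumonitis of 3 or above (read here as the grade).

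If either is met, "a detailed review of these toxicities will be performed by an independent safety committee to determine whether the trial should be stopped". The trigger therefore opens a review and does not itself stop the trial.

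Neither limb separates trametinib alone from trametinib plus GSK2141795, and the denominator is not defined. Section 13.2 makes anyone with at least one dose of trametinib evaluable for safety, which points to a pooled count. Sections 1.2 and 13.4 list the safety of trametinib with and without GSK2141795 as a secondary objective. Under sections 5.1 and 13.1 everyone starts on trametinib alone, and GSK2141795 is an option at progression or with less than a PR after 4 cycles of 28 days. On size, section 13.1 states: "The target enrollment is a minimum of 24 evaluable subjects and a maximum number of 74 if both groups accrue to the second stage".

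Section 5.2.4 recommends prophylaxis "due to an increased incidence of Shingles and infection noted on patients in this trial". Infection appears in neither limb.

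**The concern.** The combination is the less-studied regimen. Section 2.2.1.5 describes 23 patients with solid tumors, says doses had to be reduced for the combination, and lists among the dose-limiting toxicities "grade 3 chest pain with sustained ventricular tachycardia". If its events are divided by everyone treated, patients still on monotherapy enlarge the denominator without having been exposed to GSK2141795. A rate above the protocol's own limit among combination patients can then stay below the limit for the trial.

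Timing makes this worse at the first look. That look is tied to enrollment of 24 patients, whereas a patient who has not progressed cannot reach the combination before 4 × 28 = 112 days. Recent enrollees will mostly still be on monotherapy then. At stake is whether the detailed review opens when it should for the regimen that most needs it.

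**Working it through.** **Plan's own figures.** The sample sizes reproduce: 2 × 12 = 24 and 2 × 37 = 74. The efficacy rule in section 13.2 does too: exact alpha 0.0935 against the stated 10%, and power 0.902 against the stated 90%. The plan gives no operating characteristics for the safety triggers, so there is no figure to reproduce there.

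**Inputs from the documents.** Limits of more than 20% and more than 10% (13.1); 24 to 74 subjects (13.1).

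**Assumptions.** The number crossed over, m, and the true event rate on the combination, p, are not in the documents, so ranges are used. The main case has no qualifying events on monotherapy.

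**Trigger counts.** The smallest count strictly above fraction f of n is k(n, f) = floor(n × f) + 1.

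- More than 20%: floor(4.8) + 1 = 5 of 24; floor(14.8) + 1 = 15 of 74.
- More than 10%: floor(2.4) + 1 = 3 of 24; floor(7.4) + 1 = 8 of 74.

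**Observed combination rate needed under pooling (20% limb, N = 24).** 5/6 = 83%; 5/12 = 42%; 5/18 = 28%; 5/22 = 23%.

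**Probability of triggering.** Pooled: P(Bin(m, p) ≥ k(N, 0.20)). Combination-only: P(Bin(m, p) ≥ k(m, 0.20)). With p = 0.30:

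| N | Crossed over (m) | Pooled count | Pooled probability | Combination-only count | Combination-only probability |
|---|---|---|---|---|---|
| 24 | 6 | 5 | 0.011 | 2 | 0.580 |
| 24 | 12 | 5 | 0.276 | 3 | 0.747 |
| 24 | 18 | 5 | 0.667 | 4 | 0.835 |
| 24 | 22 | 5 | 0.835 | 5 | 0.835 |
| 74 | 37 | 15 | 0.113 | 8 | 0.905 |

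The first row by hand: pooled, 6 × 0.3⁵ × 0.7 + 0.3⁶ = 0.0102 + 0.0007 = 0.011; combination-only, 1 − 0.7⁶ − 6 × 0.3 × 0.7⁵ = 1 − 0.1176 − 0.3025 = 0.580.

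**Sensitivity to p.** With 12 of 24 crossed over, pooled versus combination-only is 0.073 versus 0.442 at p = 0.20, and 0.562 versus 0.917 at p = 0.40.

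**Sensitivity to monotherapy events.** A 1% grade 4 rate on monotherapy moves the pooled values at p = 0.30 only slightly: 0.026, 0.323, 0.700 and 0.854 for m = 6, 12, 18 and 22 of 24, and 0.167 for 37 of 74.

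**The 10% limb.** With 10 of 24 crossed over and p = 0.20, pooled needs 3 events (0.322) and combination-only needs 2 (0.624).

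**Cost in extra reviews.** For m ≤ 9, floor(0.1 × m) + 1 = 1, so a single event trips the 10% limb. With m = 6 and a true rate of 5%, the probability is 1 − 0.95⁶ = 0.265. With m = 10 and a true rate exactly at the 10% limit, two events are needed and the probability is 1 − 0.9¹⁰ − 10 × 0.1 × 0.9⁹ = 0.264.

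**The case against.** **Dilution depends on a fraction the plan does not give.** At the design response rates of 5% to 20% (13.2), as many as 80% to 95% of patients might become eligible for the combination. If nearly all take it, the two counts almost coincide: 5 events either way with 22 of 24, and 14 versus 15 events with 67 of 74. This stands. A reader might infer that the trigger would usually miss a combination excess; the documents support that only when about half or fewer have crossed over.

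**Pooling is inferred.** The text says only that the limits apply to subjects. True, but a denominator that must be inferred is part of the problem.

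**Splitting raises more alarms.** It does, and the working shows how many.

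**The grade 4 limb.** A reader might infer from section 2.2.1.3 ("17 patients had grade 3 diarrhea, and none had grade 4 diarrhea") that this limb can hardly be reached. That count is for 2 mg monotherapy, among about 320 subjects with diarrhea. The same section reports four grade 4 rash events, and neither figure describes the combination. Nor is it a defect that a true pooled rate of 10% or 15% would seldom trip a limit of more than 20%: those rates are below the limit. The choice of grade is a clinical judgement.

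**Events outside the list.** A reader might infer that infection, cardiac events and deaths go unwatched. They do not. The DSMB reviews safety on its own schedule (13.1) and looks for unexpected or more serious effects (Appendix D), interim safety data are examined continuously (13.2), deaths and serious events go through expedited reporting (7.3.3), and LVEF and QTc have their own rules (6.1.7, 6.1.8). Section 2.2.1.5 also says all dose-limiting toxicities were reversible on interruption. What stands is narrower: section 5.2.4 reports an infection signal in this trial, and the trigger list does not mention it.

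**Conclusion.** The point holds for the denominator. The triggers are not tied to a regimen, while the plan has a by-regimen safety objective and the second drug starts late and only in some patients. The loss of sensitivity is large when few have crossed over (1% versus 58% with 6 of 24), moderate at three quarters (67% versus 84% with 18 of 24), and nil at 22 of 24. It can persist in a larger trial: 11% versus 91% with 37 of 74. These figures rest on an assumed 30% combination rate, no monotherapy events and assumed crossover numbers. They show how the rule behaves and do not predict toxicity.

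The documents do not support reading this as a failure of safety oversight, or as grounds for changing the listed events, grades or percentages. It is a cheap improvement to the rule's definition.

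**What to change.** In section 13.1, keep the stated events and percentages and apply them to two defined denominators:

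- (a) events on trametinib alone, over all who took trametinib;
- (b) events after the first GSK2141795 dose, over all who took GSK2141795.

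Report both to the DSMB at each review, with the number crossed over. Point out to the DSMB that the infection signal in section 5.2.4 is absent from the trigger list, so that it can reconcile the two sections. No new event, grade or threshold is proposed here.

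The cost is one paragraph and one extra split in the DSMB report. The downside is more reviews while few have crossed over: with 9 or fewer, one event trips the 10% limb, and with 6 and a true 5% rate that happens 26% of the time. This is acceptable because the trigger opens a review and does not stop the trial.

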### 13.2 Sample Size/Accrual Rate

A two-stage design will be used for each group to test the null hypothesis that the extended ORR is 5% or less, versus the alternative hypothesis that the extended ORR is greater than 5% using a one-sided test with a 10% level of significance and 90% power at the alternative extended ORR of 20%. The null hypothesis of extended ORR=0.05 and the alternative extended ORR=0.20 are chosen with reference to response rate with trametinib in BRAF mutated melanoma of 22% (Flaherty *et al.*, 2012) and the response rates of single agent carfilzomib (17%) (Jagannath *et al.*, 2012) and pomalidomide (7%) (Dimopoulos *et al.*, 2012). The design is standard for such single-arm Phase II studies and appropriately minimizes the number of expected study participants when the experimental treatment is truly ineffective.

The target enrollment therefore is a minimum of 24 evaluable subjects and a maximum of 74 if both groups (biomarker positive and biomarker negative) accrue to the second stage. After testing the drug on 12 patients in each group, the trial will go to the second stage if one or more subjects respond. If the trial goes to the second stage, a total of 37 patients will be studied. If the total number of responding is more than or equal to 4, the drug is accepted. The same design as above will apply to both strata. The maximum number of this study would be 74 patients for both strata. The distribution of PFS and DOR will be summarized for each cohort using the Kaplan-Meier method. For each of these endpoints, patients will be right-censored at the date at which they were last known not to have the corresponding event.

Subjects who receive at least one dose of trametinib will be evaluable for safety. AEs will be coded according to the Medical Dictionary for Regulatory Activities (MedDRA) adverse event dictionary. The results will be tabulated to examine their frequency, organ systems affected, and relationship to study treatment. The results of laboratory assessments will be evaluated similarly. Interim safety data will be examined on an ongoing basis to ensure subject safety.

Exploratory analyses of the association of response with pharmacogenomic and pharmacodynamic will be descriptively summarized. Overall, given the limited sample size these analyses will be largely hypothesis-generating.

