These studies provide the rationale for targeting MEK with trametinib in myeloma. The pre-clinical data supports the evaluation of MEK inhibitors in patients as a single-agent and in combination with an AKT inhibitor in MM for patients who fail to respond to MEK inhibition alone. The data also support the stratification of patients based on NRAS, KRAS, and BRAF mutational status and potentially MAF expression, factors that we hypothesize will influence response. Trametinib will be evaluated as single agent in a Phase II trial. GSK2141795 (AKT inhibitor) will be combined with trametinib for patients progress on treatment or who fail to respond to trametinib after 4 cycles of treatment. This period of time is anticipated to provide a reasonable estimate of the response to single-agent trametinib, as the median time to response for two active agents studied in previously conducted phase III trials (bortezomib and

lenalidomide/dexamethasone) estimated this to be 42 days (Richardson *et al.*, 2005) and 2.1 months (Dimpoulos *et al.*, 2007). Indeed in the ECOG study of low dose vs high dose dexamethasone in combination with lenalidomide, only 5 patients of 445 upgraded their response to a partial remission after 4 cycles of treatment (Rajkumar *et al.*, 2010). It is understood that given the addition of the AKTi after 4 cycles for patients who fail to achieve a PR or better, this trial will only provide an estimate of the overall response rate to single agent trametinib.

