## **5 TREATMENT PLAN**

### **5.1 Agent Administration**

Treatment will be administered on an *outpatient* basis. Reported adverse events and potential risks are described in Section 7. Appropriate dose modifications are described in Section 6.1. No investigational or commercial agents or therapies other than those described below may be administered with the intent to treat the patient's malignancy.

Patients will receive trametinib 2 mg taken orally once a day continuously of a 28 day cycle. Patients who develop progressive disease on trametinib monotherapy or achieve less than a PR

after 4 cycles of treatment will have the option to continue on trametinib with the addition of GSK2141795. Progressive disease is defined by the IMWG, however in consultation with the Principle Investigator, GSK2141795 maybe added for progression not yet meeting the IMWG criteria if the treating physician feels that it is in the best interest of the patient. The dosing of trametinib and GSK2141795 will be according to the recommended 1.5 mg trametinib and 50 mg GSK2141795 daily dosing schedule. The patient will be requested to maintain a medication diary of each dose of medication. The medication diary will be returned to clinic staff at the end of each course:

Regimen Description					
Agent	Premedications; Precautions	Dose	Route	Schedule	Cycle Length
Trametinib	Empty stomach; 1 hr before or 2hr after a meal	2mg alone OR 1.5mg in combination with GSK2141795	oral	daily	28 days
GSK2141795	Empty stomach 1 hour after a small snack and 2 hours before a meal	50mg	oral	daily	
**Doses as appropriate for assigned dose level; refer to section 6.1. Please refer to Appendix E for example drug administration regimen of combination treatment					

For patients in whom the trametinib dose during monotherapy has been reduced to 1.5 mg the dose of trametinib will not be further reduced upon the addition of GSK2141795. For patients on trametinib monotherapy who have been dose reduced to 1.0 mg, their dose will remain at 1.0 mg upon the addition of GSK2141795. No dose re-escalation is permitted in the study (except for in the events defined in section 6).

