## 10 STUDY CALENDAR

Baseline evaluations are to be conducted within 1 week prior to start of protocol therapy, unless specified differently in the study calendar. Scans and x-rays, ECHO/MUGA, and Ophthalmology exam must be done  $\leq 4$  weeks prior to the start of therapy. In the event that the patient's condition is deteriorating, laboratory evaluations should be repeated within 48 hours prior to initiation of the next cycle of therapy. If pre-study assessments were done within 3 days of treatment initiation, they do not need to be repeated for cycle 1 day 1. For subsequent cycles (2+), day 1 assessments can be completed up to 48 hrs prior to day 1. All day 15 assessments can be completed up to 48 hrs prior to day 15. Baseline myeloma disease assessment can be done  $\leq 4$  weeks prior to the start of therapy (see [11.2.1](#)). Response assessment can be done up to  $\leq 7$  days prior to the start of the next cycle to allow for treatment decisions to be made with regards to the addition of GSK2141795 for stable disease or progression prior the initiation of the next cycle.

PROCEDURES	Screen	Cycle 1-2 Single Agent (cycle=28 days)		Cycles 3+ Single Agent	Cycle 1-2 Combination		Cycles 3+ Combination	Off Study	Safety Follow-up
		Day1	Day15	At the start of every Cycle	Day1	Day 15	At the start of every cycle		
Trametinib		A-----A			A*-----A*				4 weeks (+ 3 days) after last treatment
GSK2141795					B-----B				
Informed consent	X								
Demographics	X								
Medical history	X								
Concurrent meds	X	X-----X						X	
Physical exam	X	X		X	X		X	X	
Vital signs	X	X	X	X	X	X	X	X	
Height	X								
Weight	X	X	X	X	X	X	X	X	
Performance status	X	X	X	X	X	X	X	X	
CBC w/diff, plts	X	X	X	X	X	X	X	X	
Fasting serum chemistry a	X	X	X	X	X	X	X	X	
TSH	X				X		X i	X	
Serum viscosity m	X								
ECG b	X	X	X	X		X		X	
Echocardiogram or MUGA	X	Every 12 weeks (use same methodology for baseline and follow up).							
Ophthalmology exam l	X	as clinically indicated k							
Visual acuity exam k	X	X		X	X		X	X	
Adverse event evaluation		X-----X						X	X i
Myeloma disease assessment c (section 11.2.1)	X	Assessments are repeated every 4 weeks. Documentation must be provided for patients removed from study for progressive disease.						X	

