Progressive disease	
3. Increase of <math>\geq 25\%</math> from lowest response value in any one of the following:
 
 
1. Serum M-component (the absolute increase must be <math>\geq 0.5</math> g/dL) and/or
 
2. Urine M-component (the absolute increase must be <math>\geq 200</math> mg/24 h) and/or
 
3. Only in patients without measurable serum and urine M-protein, the difference between involved and uninvolved FLC levels. The absolute increase must be <math>> 10</math> mg/dL
 
4. Only in patients without measurable serum and urine M-protein and without measurable disease by FLC levels, bone marrow plasma cell percentage (absolute % must be <math>\geq 10\%</math>)
 
5. Definite development of new bone lesions or soft tissue plasmacytomas or definite increase in the size of existing bone lesions or soft tissue plasmacytomas
 
6. Development of hypercalcemia (corrected serum calcium <math>> 11.5</math> mg/dL) that can be attributed solely to the plasma cell proliferative disorder
 

All relapse categories (CR, sCR, VGPR, and PD) require two consecutive assessments made at any time before the institution of any new therapy; complete response and PR and SD categories also require no known evidence of progressive or new bone lesions if radiographic studies were performed. VGPR and CR categories require serum and urine studies regardless of whether disease at baseline was measurable in serum, urine both or either. Radiographic studies are not required to satisfy these response requirements. BM assessments need not be confirmed. For progressive disease, serum M-component increases of  $\geq 1$  gm/dl are sufficient to define response if starting M-component is  $\geq 5$  g/dl.

IMWG clarification for coding PD: Clarified that BM criteria for PD are to be used only in patients without measurable disease by M protein and by FLC levels. The 25% increase refers to M protein, FLC, and BM results, and does not refer to bone lesions, soft tissue plasmacytomas or hypercalcemia. Note the lowest response value does not need to be a confirmed value.

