### 13.5.2 Evaluation of Response

All patients included in the study will be assessed for response to treatment, even if there are major protocol treatment deviations or if they are ineligible. Each patient will be assigned one of the following categories: 1) stringent complete response, 2) complete response, 3) very good partial response 4) partial response, 5) minimal response 6) stable disease, 7) progressive disease, 8) early death from malignant disease, 9) early death from toxicity, 10) early death because of other cause, or 11) unknown (not assessable, insufficient data).

All of the patients who met the eligibility criteria (with the possible exception of those who received no study medication) will be included in the main analysis of the response rate. Patients in response categories 7-10 should be considered to have a treatment failure (disease progression). Thus, an incorrect treatment schedule or drug administration does not result in exclusion from the analysis of the response rate.

All conclusions on treatment efficacy will be based on all eligible patients. Sub-analyses for objective response rate will be performed on all patients meeting the eligibility criteria, who have signed a consent form, and have begun study drug treatment, and had at least one follow-up assessment or progressive disease. This analysis will clearly report the reason for exclusion that may be based on major protocol deviations such as early death due to other reasons, early discontinuation of treatment, major protocol violations, etc. Further, the 95% confidence intervals will be provided.

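### The primary ORR has no cut at the addition of GSK2141795 and is tested under an undefined name, and combination PFS has no clock or progression reference of its own

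*Combined protocol and SAP*

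**What the plan says.** **Intent.** Section 2.3 accepts that, because the AKT inhibitor is added after 4 cycles for patients below PR, "this trial will only provide an estimate of the overall response rate to single agent trametinib". Section 13.1 presents the GSK2141795 phase as a secondary objective. Section 13.2 takes its 5% and 20% rates from trametinib in melanoma and from carfilzomib and pomalidomide. Section 13.3 describes both groups as receiving trametinib.

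**Definition.** Section 13.1 defines ORR as the number of patients with confirmed PR or better, "divided by the number of patients in the applicable group (biomarker positive or negative". It has no limit by time or by treatment. Section 13.2 then uses the two-stage design "to test the null hypothesis that the extended ORR is 5% or less". The term extended ORR appears five times in that section and is not explained.

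**Switching.** Patients with progression, or with less than a PR after 4 cycles, may add GSK2141795 and stay on study. Two routes need no IMWG progression. The study calendar times response assessment to allow decisions "with regards to the addition of GSK2141795 for stable disease or progression". Section 5.1 says that, after consultation, "GSK2141795 maybe added for progression not yet meeting the IMWG criteria".

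**Combination endpoints.** Combination ORR uses the M-protein level at addition as a new baseline (13.1, 13.4). Combination PFS and DOR are also secondary objectives, but 13.4 defines each endpoint once. PFS runs from the start of treatment. DOR runs from the first recorded CR or PR. Progression for DOR is judged against the smallest value since treatment started, and 11.2.2 measures the rise "from lowest response value in any one of the following".

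**The concern.** The acceptance rule has its planned error rates for trametinib only if it counts responses to trametinib alone. Section 13.5.2 says: "Patients in response categories 7-10 should be considered to have a treatment failure (disease progression". That covers patients whose recorded category is progressive disease. Stable disease is category 6, outside that range. A patient who switches with stable disease, or with a rise short of IMWG progression, and then reaches a confirmed PR therefore fits the 13.1 definition as written. Whoever programs the endpoint must choose a reading, and the text does not choose. The choice should be made before responses are known.

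The combination endpoints have a separate problem. If treatment start means the first trametinib dose, the single PFS definition can place the event before the combination begins.

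**Working it through.** **1. The plan's own design.** Inputs from 13.2: n1 = 12, continue if at least 1 response; n = 37, accept if at least 4; null 5%, alternative 20%; one-sided level 10%, power 90%.

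P(accept | p) = Σ over x = 1 to 12 of P[Bin(12, p) = x] × P[Bin(25, p) ≥ 4 − x]

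| Stage 1 responses | p = 0.05 | p = 0.20 |
|---|---|---|
| 1 | 0.3413 × 0.1271 = 0.0434 | 0.2062 × 0.9018 = 0.1859 |
| 2 | 0.0988 × 0.3576 = 0.0353 | 0.2835 × 0.9726 = 0.2757 |
| 3 | 0.0173 × 0.7226 = 0.0125 | 0.2362 × 0.9962 = 0.2353 |
| 4 or more | 0.0022 | 0.2054 |
| P(accept), unrounded sum | 0.0935 | 0.9024 |

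The design reproduces and meets its targets. Solving P(accept) = 0.10 gives p = 0.0512, so there is little slack above 5%.

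**2. Illustration of the literal reading.** The documents give neither a myeloma response rate for the combination nor the expected uptake, so both are assumed. Let the true trametinib ORR be 5%. Let f be the share of non-responders who switch without IMWG progression, and c the share of those who reach a countable PR. The counted rate is p = 0.05 + 0.95 × f × c. The expected number of such switchers among 37 is 37 × 0.95 × f, which is 3.5, 7.0 and 10.5 for f = 0.1, 0.2 and 0.3.

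Column A counts combination responses at both stages. Column B lets only monotherapy responses open stage 2, but counts all responses at the end: P(total ≥ 4) − P(no monotherapy response in the first 12 and total ≥ 4). The documents do not say when the stage 1 rule is read, so both are shown.

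| c | f | p | A | B |
|---|---|---|---|---|
| 0.05 | 0.1 | 0.0548 | 0.119 | 0.114 |
| 0.05 | 0.2 | 0.0595 | 0.148 | 0.136 |
| 0.05 | 0.3 | 0.0643 | 0.179 | 0.158 |
| 0.01 | 0.1 | 0.0510 | 0.098 | 0.098 |
| 0.01 | 0.2 | 0.0519 | 0.103 | 0.102 |
| 0.01 | 0.3 | 0.0529 | 0.109 | 0.106 |

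**3. Does other text supply the cut?** Section 11.2.2 says that the categories it lists "require two consecutive assessments made at any time before the institution of any new therapy". The list is CR, sCR, VGPR and PD. It omits PR, and GSK2141795 is not called new therapy. If it were, the same clause would bar those responses from the combination ORR, which 13.4 defines by reference to 13.1 and 13.5.2. The separate combination ORR shows intent but does not say that its responders are excluded from the primary count.

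**4. Combination PFS and DOR, if treatment start means the first trametinib dose.**
- Switch at IMWG progression: the PFS event precedes the first combination dose.
- Switch for less than a PR after 4 cycles: about 4 × 28 = 112 days, or 16 weeks, of monotherapy time enters combination PFS.
- Progression reference: the lowest value since trametinib start does not match the new M-protein baseline in 13.1, which 13.4 applies to ORR.
- DOR origin: the first recorded CR or PR works for anyone without a monotherapy response. It fails only for a patient who responded on monotherapy, progressed and responded again.

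**The case against.** The strongest reply is that single-agent intent is plain. The rationale, the choice of reference rates, the singular drug that 13.2 says is tested and accepted, and the secondary status of the combination all point one way. On this view the defect is one unexplained adjective and one missing sentence. The point about intent stands. A reader might infer that extended means extended into the combination phase, so that the trial plans to pool both regimens. Nothing in the documents links the word to GSK2141795, and the evidence on intent runs against pooling. But intent is not the counting rule, and the rule as written admits the other result.

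It is also fair that the inflation rests on assumed inputs and that the lowest case, 0.098, stays within 0.10. A reader might go further: if half of non-responders added GSK2141795 and 20% of them responded, p = 0.05 + 0.95 × 0.5 × 0.2 = 0.145 and P(accept) = 0.73. The documents support neither input, and 13.5.2 already treats patients classed as progressive disease as failures.

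On PFS and the progression reference, treatment start can be read regimen by regimen. The study calendar restarts cycle numbering for the combination, and 13.1 speaks of a new treatment schedule until further progression. Under that reading the mismatch disappears. The text does not say which reading applies. These endpoints are descriptive and drive no decision.

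**Conclusion.** The concern holds as a gap between intent and rule. It is worth fixing but not fatal, and the sample size is sound. As written, 13.1 and 13.2 allow some combination responses to be credited to trametinib at the final count and, depending on when it is read, at the stage 1 rule. How far the level would rise is unknown. On the assumptions shown it runs from 0.098 to 0.18, against a planned 0.10 and an attained 0.0935. Only the 5.12% threshold is free of those assumptions.

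The PFS and progression-reference problem is conditional on treatment start meaning trametinib start. A reader might conclude that combination DOR has no starting point at all. That is too strong: the stated origin fails only for patients who respond again after a monotherapy response and progression.

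**What to change.** 1. In 13.1 and 13.2, replace extended ORR by ORR. Define it as confirmed PR or better against the original baseline, with both consecutive assessments made before the first GSK2141795 dose. State that patients who add GSK2141795 without such a response are non-responders at both stages.
2. In 13.4, state that combination PFS starts at the first GSK2141795 dose, that combination PFS and DOR take their baseline and nadir from that point, and that combination DOR starts at the first response recorded after it.

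The cost is wording in three sections. The 12 and 37 patients per group, the boundaries, the visits and the treatment rules stay as they are, and the dates and M-protein values are already collected. The downside is that fewer responses may count toward acceptance than under the literal text, including a PR seen once but not yet confirmed when GSK2141795 is added.
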